Frozen samples of rinsed endocervical brushings in *RNAlater* (Qiagen) will be thawed for quantitative real-time PCR. After total RNA is isolated and purified, it will be reverse transcribed into cDNA using primers. Primers for PGRMC1 and PGRMC2, mPR α and β , and PGR will be created using Primer Express software [Applied Biosystems (ABI), Foster City, CA, USA]. The primer and probe sequences for PGRMC1 and PGRMC2 have been validated recently in the macaque ovary by comparing the values obtained from real-time PCR with microarray data[61]. Transcript levels in each sample will be quantified against a five-point standard curve. Samples from similar points in the cycle will be pooled. The real-time PCRs will be performed in MicroAmp Fast Optical 96-well plates on an ABI 7500 Fast Real-time PCR System.

5. Mucus Rheological Characteristics

Once mucus samples have been evaluated by mucus score and sperm penetration (#2 and #3 above), the remaining, de-identified samples will be sent to the Complex Fluids and Soft Solids Laboratory at Oregon State University. OSU will only receive samples that are de-identified and coded by the subject number so that their tests and analysis can be correlated to serum hormone levels and results from #2-3 above. Labels on the samples will contain the subject number, the sample number (visit number) and the date the sample was originally obtained. The data returned would both be aggregated data of samples pooled from similar time points as well as data sorted by subject in order to account for inter-subject variability. OSU will use the same coding system as OHSU (subject number).

Led by [name], the lab specializes in developing both theoretical and experimental methods to study complex fluids, soft solids, miscible fluid interactions, and biological systems. They will use both sheer and extensional rheological techniques to provide detailed mechanical characterization of the cervical mucus samples. These will be performed on samples that are otherwise destroyed and will be destroyed following testing. This mechanical data will be correlated to conventional mucus scores.

6. Ion Content

Following mucus collection, an aliquot of the coded mucus may be sent to the OHSU elemental analysis core lab to measure ion content of mucus. The lab will only receive samples that are coded by the subject number so that their tests and analysis can be correlated to serum hormone levels and results from #2-3 above. Labels on the samples will contain the subject number, the sample number (visit number) and the date the sample was originally obtained. The elemental analysis core lab is an on campus facility run by [name] Ph.D. that provides quantification of ions such as sodium, calcium in biological

samples. Read out will be used to help understand changes in mucus composition due to hormonal fluctuations.

1.3.3 Subject Recruitment and Compensation

We will recruit subjects from the Portland metro area. Most of our enrollment will likely be in response to notifications of research opportunities posted on campus (print, flyers, and on-line), and through community sources soliciting volunteers and study participants (e.g., Craig's List). Subjects will be reimbursed \$45 per collection and \$250 for the leuprolide acetate injection. In the artificial cycles, we will give a 100 dollar bonus for completing each 24 cycle in order to additionally compensate subjects for the time spent at OHSU between 2 –hour collections. Total compensation for completion of all aspects of the study will be \$2000.

1.3.4 Description of drugs and devices to be studied

GnRH agonist: Lupron (leuprolide acetate) is FDA-approved for use in men for the palliative treatment of advanced prostate cancer. Lupron belongs to the GnRH agonist class of drugs. In addition to prostate cancer, Lupron is approved for use in women for the management of endometriosis and for fibroid surgery to improve anemia resulting from vaginal bleeding due to fibroids. Lupron is also approved for use in children for the treatment of central precocious puberty[62]. Our proposed use of Lupron is unapproved because we plan to use it in healthy women, which represents a different patient population. Our reason for using it in a different patient population is not to support FDA approval for a new indication, but is based on purely scientific reasons. As this is a small prospective study, to be able to study the outcomes in a crossover fashion increases the statistical power and reliability of results.

Using Lupron will allow us to determine what happens to cervical mucus when the menstrual cycle is stopped in young women thus mimicking a menopausal state, and what happens when E₂, P₄ and NET are added back in the absence of ovarian processes (i.e. follicle growth, corpus luteum development and function). Lupron act by down regulating GnRH receptors in the pituitary, thus inhibiting gonadotropin release. This mechanism of action is the same in everyone receiving leuprolide acetate, so the risks of its use in women with endometriosis or fibroids are a good surrogate for the expected risks of its use in healthy women. The dose of Lupron selected (11.25 mg) is the FDA approved 3-month dose used in women. Moreover, higher doses of leuprolide acetate are used safely (up to 30 mg for 3 month formulation). Thus, the use of Lupron is not expected to significantly increase the risks to subjects.

Estradiol: Transdermal E₂ doses were selected to in order to reproduce circulating E₂ levels consistent with a normal menstrual cycle and not to maintain replacement levels of hormone. We are assuming that absorption of E₂ from multiple patches will be linear. The form of E₂ in the patches is identical to endogenous E₂ from the ovaries, and the transdermal route of administration is preferable as it avoids the first pass effect in the liver and thus is more physiologic than oral administration[49].

The transdermal E₂ patches will be used at higher than United States Food and Drug Administration (FDA)-approved doses during the .3 mg patch days. However, subjects will be at this level for a short period of time. The amount of E₂ delivered at the highest dose (0.3 mg/day on days 7-9, 28-30) is within the normal physiologic range of E₂ secreted by the ovary during the menstrual cycle (0.07-0.5 mg/day, Vivelle-Dot package insert), so it is anticipated that even at the highest doses subjects will not be exposed to circulating E₂ levels that exceed what they are routinely exposed to during their menstrual cycle. Because the form of E₂ in the patches is identical to natural E₂, the route of administration allows for physiologic E₂ delivery, the subjects will only

be acutely exposed to unapproved doses, and our doses are anticipated to cause circulating E₂ levels similar to what the subjects are routinely exposed to during their menstrual cycle, we do not anticipate a significant increase in risk to the subjects by our proposed unapproved use of the transdermal E₂ patches. In fact, this replacement schedule was used in a previous study and E₂ peak levels were closely aligned to natural cycle peaks (mean E₂ levels 210 pg/ml in artificial vs 230 pg ml in natural cycles)[48].

Progestins: Progesterone is widely used in treatment of preterm labor as well as in support of *in vitro* fertilization cycles. We chose oral micronized progesterone to maintain the luteal phase as this is more tolerable than daily IM injections to patients. Approximately 200 mg of oral micronized progesterone is needed to reach mid luteal phase levels in premenopausal women[63]. Studies have been conducted with progesterone at much higher doses (300, 600, 1200 mg oral micronized) and no serious adverse effects were found at these higher levels[65].

Norethindrone (NET) is one of the most widely studied progestins among contraceptive steroid hormones with no associated serious adverse events and no upper dose limits known to cause toxicity[66,67]. Metabolic studies on NET alone have shown negligible effects on metabolic measures such as lipid levels, carbohydrate metabolism. They have been shown to have little or no effect on coagulation factors and when used without estrogen does not increase the risk of VTE. Norethindrone and its acetate ester derivative norethindrone acetate are often packaged with Ethinyl Estradiol in common oral contraceptive formulations. These “first generation” pills are some of the oldest FDA approved combined oral contraceptive pill formulations with decades of population data. VTE risk represents the most common serious complication of oral contraceptive pills with a 3 to 4 fold increase in the baseline VTE risk of 3-4/10,000 in oral contraceptive users[68].

1.3.5 Admission Procedure

Potential study subjects will undergo a telephone screen by the study PI or the OHSU Women’s Health Research Unit’s (WHRU) recruitment specialist. All study procedures will be performed in the WHRU outpatient Clinic. Following confirmation of study eligibility and informed written consent by either PI or study staff, confirmation of ovulatory status by serum progesterone level during days 18-25 of their menstrual cycle. The OHSU research pharmacy will be utilized for any and all drug dispensing during the study.

A computer-generated algorithm through the OHSU research pharmacy will perform randomization. Treatment allocation and blinding will occur at the end of the artificial study and prior to the start of the randomized cycle (visit 17). Blinding will single blinded so that the researcher collecting the mucus and performing the mucus scoring and sperm penetration tests does not know the patient status. The patient will know their status and will be given strict instructions to not inform the researcher of their allocation group during this part of the study. We will ask study patches during this time to be worn during non-visible areas. We chose this design because we are unable to provide placebo estrogen patches. However, we feel that this single-blinding design is acceptable, as patient knowledge of their status should not affect mucus scores or serum hormone levels.

1.3.6 Follow-up procedure

All data for this study will be collected during scheduled visits to the Women’s Health Research Unit. (see study flow figure). Our research unit has been highly successful in recruitment, enrollment and retention of subjects as part of our screening process, ease in scheduling, and appropriate compensation for study procedures.

1.3.7 Criteria for discontinuation

Patients have the right to withdraw from the trial at any time on their own request for any reason; the reason for withdrawal will be recorded in detail. No further data will be obtained from the patient once withdrawal occurs. Any data obtained up to this point will be analyzed in accordance with intention to treat.

The Data and Safety Monitoring Board (DSMB) for the WHRU at OHSU will meet on an as needed basis if any serious adverse events related to the study protocol are reported by the investigator.

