The study will begin with the first day of menstruation following enrollment. This cycle will be untreated but monitored and sampled (see figure 2 and section 1.3.3 for sample collection schedule). In order to determine points corresponding to late follicular and ovulation in these women, subjects will be provided with Clearblue® Ovulation Test (Inverness Medical Innovations, Inc., Waltham, Massachusetts). The fertility monitors test for urinary metabolites of LH, which will aid in staging of the menstrual cycle. At the end of the natural cycle treatment (menses), subjects will receive the gonadotropin releasing hormone (GnRH) agonist Lupron® (leuprolide acetate; Abbvie, Chicago, IL) in a 11.25 mg single injection which is sufficient for 3 months of continuous suppression. At 3 weeks, a visit will occur where an additional blood aliquot will be obtained and sent to the endocrine lab to confirm suppression. A phone call following confirmation will be made to instruct the subject to begin patches. We have previous experience with this model that shows ovarian suppression is reliably achieved at 21 days[48]. After confirmation of ovarian suppression and collection of baseline serum samples, all subjects will undergo replacement of endogenous estrogen with patches.

Transdermal E₂ patches changed twice weekly (Vivelle-Dot®, Noven Pharmaceuticals Inc.; Miami, FL) will be used to replace E₂, with a 0.1 mg/day transdermal dose having been previously shown to restore circulating E₂ levels in ovarian-suppressed women to 89 ± 38

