pg/ml[49], levels comparable to the late follicular and luteal phases of natural cycles[50,51]. Women will be kept at this level until prior to a randomized intervention at which point the day prior we will bring the women to mid-cycle levels (.3 mg/day). Levels of E₂ in normal women during the mid-cycle surge have been reported to be 335 ± 21 pg/ml [51] or approximately 3 times the E₂ concentrations measured with a 0.1 mg/day transdermal E₂ dose[49]. Pharmacokinetic data of E₂ patches demonstrates that half-life is approximately 5.9-7.7[52]. Again previous use of this replacement schedule demonstrates that these levels approximate serum hormone levels of normally cycling women[48]. In between interventions the subject will be maintained at the .1 mg /day level to prevent menopausal symptoms. At the end the subject will be placed on oral micronized P₄ (200 mg/day) for 5 days to trigger a withdrawal bleed. This dose causes circulating P₄ levels similar to those detected during the luteal phase of the menstrual cycle[56].

Table 3: Sample Collection Schedule for Natural Cycles.

Experimental Cycle	Phase of Cycle	Days of Collection
Natural Menstrual Cycle	Early Follicular	Days 3-5
	Mid Follicular	Days 7-9
	Late Follicular	Days 11-13
	Ovulation	Days 0-1 Post LH-Surge ("Peak" fertility home test result)
	Mid Luteal	Days 6-9 Post LH Surge

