For the intervention phase women will be randomized to receive two different interventions twice to assess the effects of a single dose of oral progestin, Norethindrone (NET) versus estrogen withdrawal only. The dose of NET .35 mg is the same dose found in commercially sold oral progestin-only contraceptives[57]. During the intervention cycles, women will be started at the .1 mg dose. After at least 5 days the subject can undergo an intervention. The day prior to the intervention the subject will have her patches increased to the .3mg level. On the day of intervention that subject will either leave the patches on and take a NET pill or the subject will have the patches removed. At this point, in order to evaluate temporality of effect, we will collect several timed samples over 24 hours from initiation of intervention (see Figure 4). Following this 24-hour collection, all patients will be placed again on .1 mg patch for ~5 days as a washout. Recognizing there is some burden to allotting time to come to the visits, the subjects may schedule their next intervention a time beyond 5 days that is convenient for them. Again, we will only increase to the .3 mg the day before the scheduled intervention is to take place. All in all, the subject will receive 4 intervention/24 hours sampling periods, 2 of which will be the NET and 2 of which will be the estrogen withdrawal. See Figure 3 for replacement and collection schedule during this part of the experiment. Finally, after the progesterone withdrawal, subjects will be placed on a low dose oral contraceptive pill (.35 mcg ethinyl estradiol/1 mg norethindrone acetate) for management of side effect related to leuprolide.

Figure 3: Sampling and Hormone and Replacement Plan for Randomized Cycles

[figure not shown]
[figure not shown]

Figure 4: 24hr Sampling Schedule

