1.3.11 Number of subjects and statistical power

This is meant to be a small pilot study and as such, a power analysis was not performed. Absolute quantification is less important than relative measures. A number of ten was chosen for the study because this will provide some buffer against biological variability as well as an

estimated 70% completion rate. This sample size collection is consistent with design of similar experiments exploring biological mechanism.

We currently have enrolled 7 subjects. However, an interim analysis noted that the original protocol did not optimize patch hormone levels immediately prior to the 24-hour collection and that we did not need more data from the original “middle artificial cycle”. The data most critical to our clinical experiment is the randomized cycles and the study has been amended to optimize data collection for these points in fewer visits.

The 7 subjects enrolled under the original protocol (approved by the IRB 19 March 2015) will complete the study under that protocol and will not be affected by these changes. The remaining subjects enrolled will follow this updated protocol.

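### Section 1.3.7 ends all data collection at withdrawal with no stated exception for safety data, although a woman who leaves after the leuprolide injection is still within the depot's three-month action (at most about 3 of 10 women)

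*Combined protocol and SAP*

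**What the plan says.** Section 1.3.7 covers withdrawal at the woman's own request: "Patients have the right to withdraw from the trial at any time on their own request for any reason". The reason is to be recorded in detail. The rule on data then follows: "No further data will be obtained from the patient once withdrawal occurs". Data gathered before that point are kept and analysed by intention to treat. The same section has the DSMB meet as needed, on serious adverse events that the investigator reports.

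Section 1.3.2 (Treatment Cycles) places the injection after the untreated natural cycle: "At the end of the natural cycle treatment (menses), subjects will receive the gonadotropin releasing hormone (GnRH) agonist". It is given "in a 11.25 mg single injection which is sufficient for 3 months of continuous suppression". The same section describes a progesterone course at the end, "for 5 days to trigger a withdrawal bleed", followed by an oral contraceptive "for management of side effect related to leuprolide". It does not say whether either step applies to a woman who leaves early.

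Section 1.3.6 (Follow-up procedure) confines data collection to scheduled visits. Section 1.3.11 sets the sample at ten, in part to allow for an "estimated 70% completion rate". It adds that seven women already enrolled will finish under the original protocol, which is not among the documents.

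**The concern.** The rule treats stopping the sampling and ending all contact as one event. For most procedures in this study that is harmless, because exposure stops when the woman stops attending. A depot injection is different: it cannot be taken back, and its stated action outlasts any withdrawal in the following three months. A woman who leaves because she tolerates the suppressed state badly has her reason noted on the day. Nothing in the available text then provides for learning whether the problem resolved, worsened or was followed by something new.

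The setting gives this some weight. The women are healthy volunteers, and section 1.3.4 itself describes the use of leuprolide in them as unapproved. At stake is patient safety and the completeness of the adverse-event record. No planned efficacy estimate is affected.

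**Working it through.** **Inputs from the documents.** Ten women; 70% completion; seven already enrolled under the original protocol (1.3.11). One injection with three months of action, and a suppression visit at 3 weeks, day 21 (1.3.2). Artificial cycle starting 21 to 28 days after injection, and interventions at least 5 days apart (1.3.3). At least 5 days on the lower patch level before an intervention, four collections of 24 hours each, and about 5 days of washout after each (1.3.2).

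**Assumptions.** Day 0 is the injection. Three months is taken as 84 to 91 days (12 to 13 weeks). The 5-day gap runs from the end of one collection to the start of the next. There is no power-based figure to reproduce, since section 1.3.11 says that no power analysis was done.

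**How many women**
- Non-completers: 10 × (1 − 0.70) = 3.
- Women who leave during the untreated natural cycle have had no leuprolide. If f is the share of dropouts that come after the injection, those affected number 3 × f. The documents do not give f. For f = 0, 0.25, 0.50, 0.75 and 1 the result is 0, 0.75, 1.5, 2.25 and 3 women.
- If the total stays at ten, this version governs 10 − 7 = 3 women, and 3 × 0.30 = 0.9, about 1.

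**How long unobserved**
- Leaving at the week-3 visit: 84 − 21 = 63 to 91 − 21 = 70 days.
- Leaving after the earliest first intervention: it starts on day 21 + 5 = 26 or 28 + 5 = 33 and ends on day 27 or 34. That leaves 84 − 34 = 50 to 91 − 27 = 64 days.
- Completing on the minimum schedule: from an artificial-cycle start on day 21, the collections run on days 26–27, 32–33, 38–39 and 44–45, so the last sampling visit is day 45. From a start on day 28 it is day 52. That leaves 84 − 52 = 32 to 91 − 45 = 46 days.

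**What the withdrawal rule itself adds.** Against a completer on the minimum schedule, leaving at day 21 adds 45 − 21 = 24 to 52 − 21 = 31 unobserved days. Leaving after the first intervention adds 45 − 27 = 18 or 52 − 34 = 18. These differences do not depend on the assumed depot length. The remaining days are common to leavers and completers.

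**The case against.** The strongest reply is that the gap is small and not peculiar to withdrawal. Completers also finish sampling about 32–46 days before the assumed end of the depot. That stands, and it is a reason to offer the same telephone contact to everyone. Completers do, however, reach the end-of-study steps in section 1.3.2, while for leavers the text is silent.

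A reader might infer four stronger things, none of which the documents support.

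- **That some 30% of the women lose follow-up.** The 70% covers the whole study, including the untreated cycle. Non-completion is also wider than withdrawal at own request, the only case that section 1.3.7 addresses. Three of ten is a ceiling.
- **That an event in a leaver cannot reach the DSMB.** The rule limits data obtained from the patient. Nothing bars the investigator from reporting an event already known or one that a former participant volunteers. What is missing is a planned route.
- **That the tolerability results will be biased.** Sections 1.1.2 and 1.3.10 contain no tolerability outcome, so no planned estimate can be biased. Because the reason for leaving is recorded, an event that prompts withdrawal is captured, though its later course is not.
- **That the plan has no safety follow-up at all, or contradicts itself.** A data rule and a duration of drug action do not conflict logically. The text between sections 1.3.13 and 1.5 was removed, so absence can be stated only for what is visible.

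**Conclusion.** The point holds in limited form. The rule in section 1.3.7 is explicit and, in the available text, has no safety exception. A woman who withdraws after the injection and before three months is therefore still exposed, with no data collection described. This concerns 0 to 3 of ten women, or about 1 if only the remaining enrolees follow this version. Whether the original protocol has the same rule is unknown.

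The unobserved periods rest on the 84–91 day reading of three months and on the minimum schedule. Later visits would shorten the completers' figure and the figure for a first intervention taken later. Confidence is high on the wording of the rule and low on the number affected. The change is worth making because it is cheap and bears on participants' safety.

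**What to change.** Replace the sentence in section 1.3.7 with wording such as: *Withdrawal ends sampling and study interventions. Unless the woman also declines contact, adverse events, pregnancy and return of menses are collected by telephone until the end of the three-month leuprolide period, and any ongoing event is followed to its outcome.* Record two separate statuses: stops procedures, and declines all contact. Add a matching line to section 1.3.6, which now limits data to scheduled visits. The same call could be made to completers.

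Sections 1.3.2 and 1.3.7 must also be reconciled on whether the end-of-study steps apply to an early leaver. That is for the sponsor and investigator to state, and this review does not say which answer is right. The new sentence should not settle it by accident.

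The cost is a line in the consent form and a little coordinator time: one or two calls for each of at most about three leavers, and more if completers are included. The site already telephones participants to start the patches. A woman's right to refuse all contact is kept.
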